### Treatment Schedule Arm B

Table 7.1			
Induction phase (Cycles 1-12)			
Drug	Route	Dose	Schedule Each cycle is 28 days
Ixazomib	Oral	4 mg	Days 1, 8 and 15
Lenalidomide	Oral	25 mg (if CrCl >60 ml/min)	Days 1-21
		10 mg (if CrCl 30-60 ml/min)	
Daratumumab	IV	16 mg/kg	Cycles 1 and 2: Days 1, 8, 15, 22
			Cycles 3, 4, 5, and 6: Days 1, 15
			Cycles 7 and beyond: Day 1
Dexamethasone	IV/ Oral*	40 mg	Days 1, 8, 15 and 22 Arm B: Cycles 1-2
* On days when daratumumab is given, Dexamethasone is given IV over 15 minutes within 1 hour prior to daratumumab			
Maintenance Phase (Cycle 13 + up to 36 months from registration)			
Ixazomib	Oral	4 mg	Days 1, 8 and 15
Daratumumab	IV	16 mg/kg	Day 1
Cycle = 28 days			

NOTE: Once the creatinine clearance is >60 mL/min during the course of the treatment, lenalidomide can be increased to 25 mg.

### 7.2 Ixazomib

- Patients should be instructed to swallow ixazomib capsules whole, with water, and not to break, chew, or open the capsules. Ixazomib should be taken on an empty stomach, at least 1 hour before or at least 2 hours after food. Each capsule should be swallowed separately with a sip of water. A total of approximately 8 ounces (240 mL) of water should be taken with the capsules.
- Missed doses can be taken as soon as the patient remembers if the next scheduled dose is 72 hours or more away. A double dose should not be taken to make up for a missed dose. If the patient vomits after taking a dose, the patient should not repeat the dose but should resume dosing at the time of the next scheduled dose.
- Procedures for ixazomib dose reductions and delays are summarized in Section 8.2, along with the criteria that must be met for retreatment with study drug. If a dose is missed due to toxicity, the dose will not be made up.
- Oral ixazomib is supplied by Takeda Pharmaceuticals. See Section 15.1 for details on ixazomib description, formulation, storage, and accountability.

7.3 Lenalidomide (Cycles 1-12 only)

- Subjects will receive lenalidomide orally once daily on days 1-21 of the 28 day cycle.
- Lenalidomide is taken with water on a full or empty stomach. Subjects should not crush or chew capsules. Missed doses will not be made up.
- Procedures for dose reductions and delays are summarized in Section 8.3.
- Lenalidomide is commercially obtained.

7.4 Daratumumab

- Subjects will receive daratumumab intravenously weekly for 8 weeks, then every other week for 16 weeks and then every 4 weeks.
- Each subject's dose will be calculated based on the subject's weight rounded to the nearest kilogram. There is no cap on the absolute dose allowed, as long as the dose does not exceed 16 mg/kg. If a subject's weight changes by more than 10% from baseline, the dose of daratumumab will be re-calculated.
- Vital signs should be monitored extensively on Cycle 1 Day 1 before, during, and after the first infusion of daratumumab. For all other infusions, vital signs should be measured immediately before the start of infusion and at the end of the infusion.
- Missed doses will not be made up. Procedures for dose reductions and delays are summarized in Section 8.5.
- There are no planned dose reductions.
- Daratumumab is provided by Janssen. See Section 15.4 for details on daratumumab description, formulation, storage, and accountability.

**As of amendment 12:**

In the event patient is unable to come to the enrolling site for daratumumab infusion due to extenuating circumstances, commercial drug can be used for administration at a facility accessible to the patient. In that event, the treating investigator will work closely with the external provider to ensure safe and appropriate delivery of the planned dose. This instance will have to be reported to the IRB as a deviation.

- Daratumumab administration: See table below for general infusion guidelines. If patients tolerate the first 3 infusions, consideration can be given for a 90 minute infusion as per institutional guidelines. *Refer to section 9 for prophylaxis and treatment of infusion reactions*

	Dilution volume (mL)	Initial rate (first hour)	Rate increment	Maximum rate
First infusion	1000 mL	50 mL/hour	50 mL/hour every hour	200 mL/hour
Second infusion a	500 mL	50 mL/hour	50 mL/hour every hour	200 mL/hour
Subsequent infusions b	500 mL	100 mL/hour	50 mL/hour every hour	200 mL/hour

a Escalate only if there were no Grade 1 (mild) or greater infusion reactions during the first 3 hours of the first infusion.

b Escalate only if there were no Grade 1 (mild) or greater infusion reactions during a final infusion rate of  $\geq 100$  mL/hr in the first two infusions.

7.5 Dexamethasone (Cycles 1-12 for Arm A / Cycles 1 and 2 only for Arm B)

- Dexamethasone may be self-administered by the subject on an outpatient basis.
- **Arm A:**

Dexamethasone may be permanently discontinued after 12 cycles at the treating physician's discretion or sooner if needed to manage toxicity related to dexamethasone.

**Arm B:**

Dexamethasone will be discontinued after 2 cycles or sooner if needed to manage toxicity related to dexamethasone. Dexamethasone as part of infusion reaction prophylaxis may continue.

- Missed doses of dexamethasone will not be made up. Procedures for dose reductions and delays are summarized in Section 8.2.
- Dexamethasone is commercially available. Accurate records will be kept in the source documents of all drug administration (including dispensing and dosing).

7.6 Treatment at enrolling institution:

For this protocol, the patient must return to the consenting institution for daratumumab infusions as per treatment schedule and for evaluation prior to each cycle. Treatment by a local medical doctor (LMD) is not allowed **As of amendment 12: Exception noted above in 7.4.**

**As of amendment 12:**

The patient must return to the consenting institution for ixazomib evaluation at least every third cycle, provided the drug can be sent to the patient and necessary interval evaluations as required by the protocol can be completed remotely or through local healthcare facilities.

## 8.0 Dosage Modification Based on Adverse Events

Strictly follow the modifications in this table for the first **two** cycles, until individual treatment tolerance can be ascertained. Individual drugs can be dose reduced as per the table below depending on the adverse event attribution. If the toxicity is attributable to one drug, only that needs to be dose reduced. If overlapping toxicities are observed, the dose reductions can be alternated between the suspected drugs, starting with the drug most likely related to the adverse event. Thereafter, these modifications should be regarded as guidelines to limit to mild-to-moderate, but not debilitating, side effects. If multiple adverse events are seen, administer dose based on greatest reduction required for any single adverse event observed. Reductions apply to treatment given in the preceding cycle and are based on adverse events observed since the prior dose.

**NOTE: If ixazomib, lenalidomide or daratumumab is discontinued, the patient can continue on the other drugs, unless specified otherwise in the dose modification tables. If all three are discontinued, the patient will go to event monitoring (Section 4.2).**

**ALERT: ADR reporting may be required for some adverse events (See Section 10)**

8.1 Dose Levels for each drug in the combination  
 (Based on Adverse Events in Tables 8.2-5)

**NOTE:** Toxicities attributable to dexamethasone should lead to dose reduction only for dexamethasone.

Table 8.1 Dose reduction steps				
Step	Ixazomib	Lenalidomide	Daratumumab	Dexamethasone
0	4 mg	25 mg	NA	40 mg
-1	3 mg	15 mg		24 mg
-2	2.3 mg	10 mg		12 mg
-3	Discontinue	5 mg		4 mg
-4	Discontinue	Discontinue		Discontinue

8.11 Instruction for initiation of a new cycle of therapy or restarting therapy after interruption during a cycle for toxicities

A new cycle of treatment may begin on the scheduled Day 1 of a new cycle if:

- The ANC is  $\geq 1000/\mu\text{L}$
- The platelet count is  $\geq 75,000/\mu\text{L}$
- Any other non-hematologic treatment -related adverse event that may have occurred has resolved to  $\leq$ Grade 1 or baseline severity.

If these conditions are not met on Day 1 of a new cycle, the subject will be evaluated weekly and a new cycle of therapy will be held until the toxicity has resolved as described above.

If any drug dosing was halted during the previous cycle and was restarted with a one-level dose reduction without requiring an interruption for the remainder of the cycle, then that reduced dose level will be initiated on Day 1 of the new cycle.

If any drug dosing was omitted for the remainder of the previous cycle or if the new cycle is held due to known hematologic toxicity newly encountered on the scheduled Day 1, then the new cycle will be started with a one-level dose reduction. If a new cycle of therapy cannot be restarted within 4 weeks of the scheduled Day 1 due to non-resolution of drug related toxicities, the patient will be removed from protocol therapy and will go to event monitoring.

→ → Use the NCI Common Terminology Criteria for Adverse Events (CTCAE) version 4.0\* unless otherwise specified ← ←

## 8.2 Dose modifications for ixazomib based on adverse events during a cycle

CTCAE System/Organ/Class (SOC)*	ADVERSE EVENT	ACTION**
Investigations	If platelet count $<30 \times 10^9/L$ or ANC $<1.0 \times 10^9/L$ or ANC $>1.0 \times 10^9/L$ (up to LLN) with fever (temperature $>38.5^{\circ}C$ )	Days 2-15: Ixazomib dose should be omitted on Day 8 and/or 15 as applicable Complete blood count (CBC) with differential should be followed weekly. If ANC is $\geq 1.0 \times 10^9/L$ and/or platelet counts $\geq 30 \times 10^9/L$ , ixazomib may be reinitiated with 1 dose level reduction. The subsequent cycle will use the reduced dose.
Skin and subcutaneous tissue disorders	Rash, Any skin, $\geq$ Grade 2	Omit ixazomib till rash resolves to $\leq$ Grade 1 (See Section 9.9a ). Restart at same dose. If the rash recurs, reduce dose by one dose level.
	Any skin, Grade 4	Discontinue ixazomib and remove patient from all study treatment
Nervous System Disorders	Newly developed Grade 1 peripheral neuropathy with pain, $\geq$ Grade 2 peripheral neuropathy	Reduce dose of ixazomib to the next lower dose level
Nervous System Disorders	Grade 2 neuropathy with pain or Grade 3 peripheral neuropathy	Omit ixazomib until toxicity resolves or returns to baseline. When toxicity resolves, re-initiate ixazomib at the next lower dose level.
	Grade 4 peripheral neuropathy	Permanently discontinue ixazomib.
Other	Any other non-hematological Grade 3 attributable toxicity except: Grade 3 nausea and/or emesis in the absence of optimal anti-emetic prophylaxis Grade 3 diarrhea that occurs in the absence of optimal supportive therapy Grade 3 fatigue	Omit ixazomib depending on the attribution, until resolution to Grade $\leq 1$ or baseline Restart at next lower dose. If a patient is already at the lowest drug level, go to event monitoring
	Grade 4 Nonhematologic Toxicities	Consider permanently discontinuing ixazomib – Exception if the investigator determines the patient is obtaining a clinical benefit

\* Located at [REDACTED]

\*\* Use the following to describe actions in the Action column:

➤ Omit = The current dose(s) for the specified drug(s) during a cycle is skipped. The patient does not make up the omitted dose(s) at a later time

- Hold/Delay = The current dose(s) of all drugs during a cycle is delayed. The patient does make up the delayed dose(s) when the patient meets the protocol criteria to restart drugs.
- Discontinue = The specified drug(s) are totally stopped.

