### 8.3 Dose modifications for lenalidomide based on adverse events during a cycle

CTCAE System/Organ/Class (SOC)	ADVERSE EVENT	ACTION
Blood and lymphatic system disorders	febrile neutropenia associated with fever (temperature $\geq 38.5^{\circ}\text{C}$ )	
 
• Omit lenalidomide dose.
 
• Follow CBC weekly.
 
• If neutropenia has resolved to <math>\leq</math> grade 2 prior to Day 21 and fever has resolved, restart lenalidomide at next lower dose level and continue the cycle through Day 21. If febrile neutropenia is the only toxicity for which a dose reduction is required. G-CSF may be used and the lenalidomide dose maintained.
 

Investigations	If platelet count $<30 \times 10^9/\text{L}$ or ANC $<1.0 \times 10^9/\text{L}$ or ANC $>1.0 \times 10^9/\text{L}$ (up to LLN) with fever (temperature $>38.5^{\circ}\text{C}$ )	
 
• Omit lenalidomide dose.
 
• Follow CBC weekly.
 
• Hold anticoagulation until platelets <math>> 50,000</math>
 
• If platelet count resolves to <math>\leq</math> grade 2 prior to Day 21, restart lenalidomide at next lower dose level and continue the cycle through Day 21.
 
• If neutropenia has resolved to <math>\leq</math> grade 2 prior to Day 21, restart lenalidomide at next lower dose level and continue the cycle through Day 21. If neutropenia is the only toxicity for which a dose reduction is required. G-CSF may be used and the lenalidomide dose maintained.
 

Skin and subcutaneous tissue disorders	Rash maculo papular Grade 2 or 3.	
 
• Omit lenalidomide dose. Follow weekly.
 
• If the toxicity resolves to <math>\leq</math> grade 1 prior to Day 21, restart lenalidomide at next lower dose level and continue the cycle through Day 21.
 

	Any rash Grade 4	
 
• Discontinue lenalidomide. Remove patient from all study treatment.
 
• Go to event monitoring.
 

Nervous system disorders	Peripheral sensory Neuropathy Grade 3	
 
• Omit lenalidomide dose. Follow at least weekly.
 
• If the toxicity resolves to <math>\leq</math> grade 1 prior to Day 21, restart lenalidomide at next lower dose level and continue the cycle through Day 21.
 

CTCAE System/Organ/Class (SOC)	ADVERSE EVENT	ACTION

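### Section 8.2 lets ixazomib restart within a cycle without requiring all three omission triggers to have cleared, and its fever trigger has no release condition; Section 8.3 has a narrower gap for lenalidomide

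*Combined protocol and SAP*

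**What the plan says.** All counts are in 10^9/L.

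**Ixazomib (Section 8.2, Investigations row).** Three triggers, joined by *or*, lead to omission: platelets <30; ANC <1.0; or ANC >1.0 up to LLN with temperature >38.5 °C. For Days 2–15 the action is "Ixazomib dose should be omitted on Day 8 and/or 15 as applicable", with weekly blood counts. Restart is allowed if ANC is ≥1.0 "and/or platelet counts $\geq 30 \times 10^9/L$ , ixazomib may be reinitiated with 1 dose level reduction". Temperature is not mentioned in the restart sentence.

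**Lenalidomide (Section 8.3, Investigations row).** The same three triggers apply, with a separate restart line for each count. The platelet line begins "If platelet count resolves to" grade 2 or better. The neutrophil line, once grade 2 or better is reached, runs "prior to Day 21, restart lenalidomide at next lower dose level and continue the cycle through Day 21. If neutropenia is the only", leading into the G-CSF exception. Neither line mentions the other count or fever. The febrile neutropenia row just above does carry a fever condition: "prior to Day 21 and fever has resolved, restart lenalidomide at next lower dose level and continue the cycle through Day 21".

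**How binding the tables are (Section 8.0).** "Strictly follow the modifications in this table for the first" two cycles; then "Thereafter, these modifications should be regarded as guidelines to limit to mild-to-moderate, but not debilitating, side effects".

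**New-cycle criteria (Section 8.11).** The heading covers restarting after an interruption during a cycle as well as starting a new one. The count criteria (ANC ≥1000/µL, platelets ≥75,000/µL) are introduced by "A new cycle of treatment may begin on the scheduled Day 1 of a new cycle if".

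**The concern.** When any one of several conditions stops a drug, the safe release rule is that none of them still holds. The 8.2 restart sentence does not say this. It joins two count cut-offs with *and/or* and leaves out the third trigger's distinguishing feature, fever. Other rows of the same table tie restart to resolution of the event (rash, Grade 3 neuropathy, other Grade 3 non-hematologic toxicity), so the omission here looks unintended.

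What is at stake is dosing safety and consistency between sites. With the same findings, one site could re-dose a febrile patient whose ANC is between 1.0 and LLN, and another could withhold. Both could claim to be following the table, in the two cycles where it is to be followed strictly.

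**Working it through.** The plan gives no figure to reproduce here. The check is a truth table on the wording of 8.2, followed by a comparison with the other sections.

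**1. Combinations.** Platelets (<30, ≥30) × ANC (<1.0, exactly 1.0, >1.0 to LLN, above LLN) × temperature (≤38.5, >38.5 °C) gives 2 × 4 × 2 = 16.

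**2. Omission trigger met.**
- Platelets <30: 4 × 2 = 8
- Platelets ≥30 with ANC <1.0: 2
- Platelets ≥30, ANC >1.0 to LLN, temperature >38.5 °C: 1

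The total is 8 + 2 + 1 = 11, leaving 16 − 11 = 5 with no trigger.

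**3. Restart also allowed among those 11.**

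| Reading of the restart rule | Restart fails when | Trigger met and restart allowed |
|---|---|---|
| *or* (either count adequate) | both counts low (2 combinations) | 11 − 2 = 9 |
| *and* (both counts adequate) | either count low (8 + 2 = 10 combinations) | 11 − 10 = 1 |
| whichever count was low must recover (judged on current counts) | either count low (10) | 11 − 10 = 1 |
| none of the three triggers still met | any trigger met (11) | 0 |

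The 1 that remains is platelets ≥30, ANC >1.0 to LLN and temperature >38.5 °C. For example, platelets of 60 and an ANC of 1.2 with fever meet the third omission trigger (taking LLN to be above 1.2) and already satisfy both restart cut-offs. These are combinations of findings, not patient frequencies, and the ratios depend on how the cells are chosen. The finding that does not depend on the cells is that the fever case passes under every reading of *and/or*.

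**4. Whether another section closes the gap.**
- Section 8.11: the heading mentions mid-cycle restart, but the count criteria are worded only for Day 1 of a new cycle.
- Sections 9.9b and 9.9c: therapy may resume at a reduced level once platelets or ANC, respectively, recover. This supports the *whichever count was low* reading. Neither gives a cut-off or a fever condition.
- Section 8.0, multiple adverse events: this sets the size of the dose reduction, not when to restart.

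**5. Lenalidomide.** There is no *and/or* in 8.3, each line needs its own count to reach grade 2 or better, and the febrile neutropenia row requires fever to have resolved. Two things remain. First, if both counts were low and neutropenia resolves first, the neutrophil line alone permits restart with platelets still low, and the reverse holds for the platelet line. Second, the Investigations row's own fever trigger has no fever-resolution condition. Assuming that an ANC of 1.0 or more counts as grade 2 or better (the protocol does not print the grade limits), a febrile patient with ANC between 1.0 and LLN already meets the neutrophil line. The febrile neutropenia row catches that patient only if the site classifies the event that way, and the row gives no ANC cut-off.

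**6. Reach for ixazomib.** Doses fall on Days 1, 8 and 15, and 8.11 governs Day 1. After a skipped dose, the only dose that can be resumed in the same cycle is Day 15: at most 1 per cycle, or 2 in the two strict cycles. Day 8 comes in only if a trigger arises after Day 1 and the restart decision is made before any dose has been skipped.

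**The case against.** The best case for the present text has several parts.

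- **The literal *or* reading defeats itself.** A patient omitted for platelets of 20 with an ANC of 2.0 would qualify for restart at the moment of omission, so the platelet trigger would do nothing. A reader might infer from the 9 of 11 that the protocol tells sites to re-dose in severe thrombocytopenia. The documents do not support that: the natural reading is recovery of whichever count was low, and 9.9b and 9.9c point the same way. The 9 shows loose drafting, not an instruction. This part of the objection stands.
- **A live trigger can be taken to govern each dose day.** The omission instruction applies to Day 8 and Day 15, omitting means skipping the current dose, and restart is only permitted, not required. A careful site would withhold. That is a sound way to work, but the table does not state it, and the restart sentence as written is met in the fever case.
- **The gap in 8.3 is not the same gap.** This is correct, for the reasons in step 5 of the working.
- **Practical reach is small.** From Cycle 4 the Section 4.1 schedule has one blood count per cycle, so a mid-cycle count trigger would usually need an unscheduled test, and after Cycle 2 the table is only a guideline. This limits the consequence. It does not bear on Cycles 1–2, where counts are scheduled every 14 days and the table is binding.

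**Conclusion.** The concern holds as an ambiguity with a safety consequence, not as two irreconcilable instructions. In 8.2 the restart sentence does not require all three triggers to have cleared. For a single low count, a sensible reading resolves this. For the fever trigger no reading of *and/or* does: 1 of the 11 trigger combinations passes the restart sentence even when both counts must be adequate. In 8.3 a narrower gap remains, and its fever part rests on the assumed grade limit for ANC.

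The documents give no event rates for this four-drug regimen at these cut-offs, so the number of patients or doses affected cannot be estimated. A reader might also infer that the trial's results are at risk. They are not on this account: the confirmed complete response endpoint, the 36 evaluable patients per arm and the decision rule are untouched. It is worth correcting because the rule concerns re-dosing during fever or low counts and is binding in the first two cycles.

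**What to change.** **Section 8.2, Investigations row.** Replace the restart sentence with:

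> When none of the three triggers above is still met (platelets ≥30 × 10^9/L, ANC ≥1.0 × 10^9/L, and no temperature >38.5 °C with ANC >1.0 up to LLN), ixazomib may be restarted one dose level lower.

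On the 16 combinations this leaves 0 of 11 overlaps and withholds ixazomib in 0 of the 5 where no trigger is met. A broader condition, barring restart at any temperature above 38.5 °C, would also give 0 of 11 but would withhold in 2 of the 5 (ANC exactly 1.0, or above LLN, with fever). That would be a new withholding rule, and it is not needed to close the gap.

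**Section 8.3, Investigations row.** Replace the two separate restart conditions with:

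> Before Day 21, restart lenalidomide one dose level lower only when each count that led to the omission has recovered to grade 2 or better and none of this row's three triggers is still met; then continue through Day 21.

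Keep the G-CSF and anticoagulation lines.

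**Cost.** Two table cells change, with no new tests or visits. Lenalidomide may be held longer when both counts led to the omission, because both must then recover.

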	Grade 4	
 
Discontinue lenalidomide. Remove patient from all study treatment.
 
Go to event monitoring.
 

Immune system disorders	Allergic reaction Grade 2-3	
 
Omit dose. Follow at least weekly.
 
If the toxicity resolves to <math>\leq</math> grade 1 prior to Day 15 restart at next lower dose level and continue the cycle until Day 21.
 

	Grade 4	
 
Discontinue lenalidomide. Remove patient from all study treatment.
 
Go to event monitoring.
 

Vascular disorders	Thromboembolic event $\geq$ Grade 3	
 
Omit dose and start anticoagulation; restart at investigator's discretion (maintain dose level).
 

	Hyperthyroidism or Hypothyroidism $\geq$ grade 2	
 
Omit lenalidomide for remainder of cycle, evaluate etiology, and initiate appropriate therapy.
 
See Instructions for Initiation of a New Cycle and reduce the dose of lenalidomide by 1 dose level.
 

Other non-hematologic adverse event	Other non-hematologic toxicity $\geq$ Grade 3	
 
Omit lenalidomide dose. Follow at least weekly.
 
If the toxicity resolves to <math>\leq</math> grade 2 prior to Day 21, restart lenalidomide at next lower dose level and continue the cycle through Day 21.
 

Lenalidomide dose modifications for renal impairment developing during treatment, considered not related to lenalidomide

Renal Function	Dose
CrCl 30-60 ml/min	10 mg daily
CrCl $<$ 30 mL/min (not requiring dialysis)	15 mg every 48 hours
CrCl $<$ 30 mL/min (requiring dialysis)	5 mg once daily. On dialysis days, administer the dose after dialysis

\* Located at [REDACTED]

\*\* Use the following to describe actions in the Action column:

- Omit = The current dose(s) for the specified drug(s) during a cycle is skipped. The patient does not make up the omitted dose(s) at a later time
- Hold/Delay = The current dose(s) of all drugs during a cycle is delayed. The patient does make up the delayed dose(s) when the patient meets the protocol criteria to restart drugs.
- Discontinue = The specified drug(s) are totally stopped.

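### The ixazomib neuropathy rows in Section 8.2 overlap: Grade 2 with pain, Grade 3 and Grade 4 each meet more than one action, and no rule says which governs

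*Combined protocol and SAP*

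**What the plan says.** The Section 8.2 table has three neuropathy rows for ixazomib.

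- Row 1 is triggered by "Newly developed Grade 1 peripheral neuropathy with pain, $\geq$ Grade 2 peripheral neuropathy". The action is "Reduce dose of ixazomib to the next lower dose level".
- Row 2 is triggered by "Grade 2 neuropathy with pain or Grade 3 peripheral neuropathy". The action begins "Omit ixazomib until toxicity resolves or returns to baseline", after which ixazomib restarts one level lower.
- Row 3 is triggered by "Grade 4 peripheral neuropathy" and stops ixazomib permanently.

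Lower in the same table, under the label Other, a general row for Grade 4 non-hematologic toxicity asks the investigator only to consider stopping ixazomib, with an exception for clinical benefit.

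Section 8.3 handles Grade 4 in its peripheral sensory neuropathy block as follows: "Discontinue lenalidomide. Remove patient from all study treatment", then event monitoring. The NOTE in Section 8.0 sets the default: "If ixazomib, lenalidomide or daratumumab is discontinued, the patient can continue on the other drugs", unless a dose modification table says otherwise. Section 8.0 also requires strict adherence for the first two cycles, treats the tables as guidelines after that, and ties each change to the drug held responsible.

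**The concern.** Row 1 has a floor and no ceiling, so it takes in everything that rows 2 and 3 were written to handle separately. A site treating a patient with Grade 3 neuropathy in Cycle 1 finds one row telling it to give a reduced dose and another telling it to give none. A site with a Grade 4 event finds one row that keeps ixazomib at a lower level and another that ends it for good.

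Two sites could therefore treat the same event differently and each be able to point to the protocol. That is first a patient-safety matter. It also makes it unclear what counts as a deviation in the two cycles where the tables are binding.

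**Working it through.** No plan figure is at issue within the table, so the check matches each category against the literal trigger of each row.

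| Category | Row 1: reduce | Row 2: omit, then one level lower | Row 3: permanently stop |
|---|---|---|---|
| New Grade 1 with pain | yes | no | no |
| Grade 2 without pain | yes | no | no |
| Grade 2 with pain | yes | yes | no |
| Grade 3 | yes | yes | no |
| Grade 4 | yes | no | yes |

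Three of the five categories, or three of the four from Grade 2 upward, meet two rows with different actions. Read literally, Grade 4 also meets the general Grade 4 non-hematologic row, although its place under Other suggests that it was meant for toxicities not already listed.

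**Is there a tie-break?** The only candidate is the Section 8.0 instruction to use the greatest reduction. It applies when several adverse events occur together, not when one event meets two rows. No statement gives the more specific row precedence.

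**How far does the conflict reach for Grade 2 with pain and Grade 3?** Both rows end one level lower. Section 8.11 allows a new cycle only once a treatment-related non-hematologic event is back to Grade 1 or below, or to baseline. It removes the patient from protocol therapy if that takes more than 4 weeks from the scheduled Day 1. The disagreement is therefore about doses still due in the current cycle. Ixazomib is given on Days 1, 8 and 15 (Table 7.1), and the first reduction is from 4 mg to 3 mg (Table 8.1). For an event arising between the Day 1 and Day 8 doses, at the starting dose:

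- Row 1: 4 + 3 + 3 = 10 mg in the cycle.
- Row 2, not recovered by Day 15: 4 + 0 + 0 = 4 mg.
- Row 2, recovered between Days 8 and 15: 4 + 0 + 3 = 7 mg.
- Row 2, recovered by Day 8: 4 + 3 + 3 = 10 mg.

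The rows thus differ by 0 to 6 mg out of a planned 3 × 4 = 12 mg, and not at all once the Day 15 dose has been given. At 2.3 mg the next step in Table 8.1 is discontinuation, so at that level the rows converge.

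**Grade 4.** Here the difference does not end with the cycle. Row 1 leaves ixazomib available at a lower level, subject to Section 8.11; row 3 ends it.

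**Grade 4 across the two tables.** Section 8.2 stops ixazomib and is silent on the other drugs, so under the Section 8.0 NOTE they may continue. Section 8.3 stops all study treatment. Sections 15.17 and 15.27 list peripheral neuropathy as very common for ixazomib and lenalidomide respectively, so shared or unclear attribution is foreseeable. The Section 8.0 rule for overlapping toxicities alternates dose reductions and does not address discontinuation.

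**How many patients?** The documents give no neuropathy rate for this regimen. The single-agent study in relapsed disease (Section 1.3, Study C16004) reports 20% neuropathy of any grade and one Grade 3 event among 60 patients. If that carried over:

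- Grade 3: 1/60 = 1.7%; 36 × 1/60 = 0.6 patients per arm.
- Any grade: 36 × 0.20 = 7.2 patients per arm. This is a ceiling for that source and not an estimate, because it includes painless Grade 1, which meets no neuropathy row, and painless Grade 2, which meets only one.

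No figure is given for Grade 2 with pain, and no Grade 4 neuropathy is mentioned.

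**The case against.** The strongest reply is that the rows plainly escalate: reduce, then omit and reduce, then stop. Each has a narrower trigger than the one before. The rash rows of the same table have the same layout, and reading row 1 as governing Grade 3 or Grade 4 would leave rows 2 and 3 with nothing to do. That is probably how most investigators would read it. It remains an assumption, because the protocol does not say so and asks for strict adherence in exactly the period when tolerance is being established.

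Three stronger readings are tempting, and the documents do not support them.

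- A reader might infer that a patient with persisting Grade 3 neuropathy could stay on reduced ixazomib cycle after cycle. Section 8.11 prevents this.
- A reader might infer that Sections 8.2 and 8.3 flatly contradict each other on Grade 4. They largely do not. If the event is attributed to ixazomib alone, the lenalidomide row need not apply. If both drugs are suspected, ending all treatment also satisfies the ixazomib row. Section 8.3 is also worded for sensory neuropathy, while Section 8.2 is not. What remains is a gap when attribution is shared or unclear. For Grade 4 rash, by contrast, both tables state removal from all treatment.
- A reader might infer that the overlap changes the complete response result, or undermines the FACT/GOG neurotoxicity questionnaire. Neither follows. Eligible treated patients remain evaluable under Section 16.11 unless they are major violations, stopping ixazomib does not by itself end treatment, and the stated aim of the questionnaire in Section 2.3 is quality of life.

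**Conclusion.** The overlap is real on the text and has no stated resolution. It affects Grade 2 with pain, Grade 3 and Grade 4. For the first two it concerns at most the Day 8 and Day 15 doses of the current cycle. For Grade 4 it is reduction against permanent discontinuation, which is the more serious conflict. The difference between Sections 8.2 and 8.3 is secondary.

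Few patients per arm are likely to be involved. The one severity-specific figure available gives about 0.6 Grade 3 cases per 36, assuming that a single-agent rate in relapsed disease applies here. The four-drug rate could be higher, since Section 15.47 also lists peripheral sensory neuropathy as very common for daratumumab. Taking 20% of 36, about 7, as the number affected would be wrong for the reason shown above. The point rests on patient safety and consistent conduct, not on any demonstrated effect on the primary endpoint.

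**What to change.** The sponsor should reconcile the neuropathy rows of Section 8.2 so that every grade-and-pain category falls in exactly one row, and make clear whether the general Grade 4 non-hematologic row applies to neuropathy. As a secondary clarification, Sections 8.2 and 8.3 should be reconciled on whether Grade 4 neuropathy ends one drug or all study treatment when attribution is shared or unclear. Which action is right is a clinical decision for the sponsor, and none is proposed here. The cost is a wording change to two tables; sample size, analysis and visit schedule are untouched.
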